1.1 Overview of Non-Clinical Studies

Laboratory studies indicate that cold-stored whole blood retains hemostatic ability over at least 10 days at 2-6°C, and likely longer. Spinella et al¹⁴ and Pidkoke et al¹⁵ have extensively reviewed the hemostatic capacity of cold-stored WB and the viability of platelets in this product. In those reviews, there is convincing evidence that cold-stored platelets not only retain function but that they perform better than room temperature-stored platelets in aggregation studies. Most of the studies in these reviews evaluated storage up to 7 days. However, several studies have specifically addressed platelet function in WB stored for 21 days or longer with similar findings. Jobes et al demonstrated that in unfiltered WB stored at 1-6°C, platelet counts decrease starting at day 4 and then level off and stabilize by day 7.¹⁶ Additionally, platelet function in cold stored WB as measured by platelet aggregometry showed no change in the aggregation responses to ADP and epinephrine stimulation from day 1 to day 21 of storage but did have a decline in response to collagen by day 7 and ristocetin by day 17. However, despite a gradual decline in platelet count and response to some agonists, global platelet function in the stored unit as measured by thromboelastography (TEG) was maintained within the normal range until day 14 of storage¹⁶.

Pidkoke et al. found similar results showing that refrigerated (1-6°C) WB improved impedance platelet aggregation and TEG results compared to WB units stored at 22°C for 21 days. In this study, prolongation of prothrombin time was also attenuated by refrigeration.¹⁷ Functional clotting capacity as measured by thromboelastography remained relatively stable in refrigerated units over 21 days. In studies performed at UCLA, we found similar results with TEG values maintained within the normal range for up to 35 days of storage at 1-6°C in unfiltered WB (manuscript accepted, *Journal of Trauma and Acute Care Surgery*).

Standard leukoreduction techniques for blood processing remove platelets as well as white blood cells. Our study proposes to use a platelet-sparing leukoreduction filter which has previously been evaluated for leukoreduction of whole blood (Imuflex WB-SP, Terumo).¹⁸ The filter works with a polyurethane membrane that permits passage of RBCs and platelets but impedes white blood cells. Theoretically passage through the filter could activate RBCs and platelets and target them for destruction, but this was not the case based on *in vivo* recovery of radiolabeled red cells and platelets after autologous transfusion. PRBCs, platelets, and plasma produced by the filter were tested to and confirmed to meet FDA requirements, including leukoreduction standards.¹⁸

Additionally, Strandenes et al. recently demonstrated that global platelet function as measured by ROTEM is maintained in WB that has been stored at 2-6°C for up to 21 days after filtration with this platelet-sparing filter. In that study, maximum clot firmness began to decrease by day 10-14 but remained within the reference range through day 21.¹⁹ These data provide convincing evidence that platelet function in a 10-day-old unit of filtered WB will be adequate to support hemostasis.

Optimal storage conditions for refrigerated whole blood have also been investigated. Using the platelet-sparing filter, Yazer et al studied whether whole blood should be agitated to enhance platelet function, or whether this would damage the red cells.²⁰ In this study, whole blood was maintained between 20-24°C before leukoreduction occurred within 8 hours; blood was then immediately placed in a 1-6°C refrigerator. Units then underwent infectious disease testing over 3 days, and were then delivered to the transfusion service. This timeline and storage plan is the same as that used in the proposed study. After processing, units were stored for 21 days under different rocking conditions. Based on thromboelastography and markers of hemolysis, the recommended storage condition for cold stored whole blood is stationary for up to 10 days. Importantly, platelet function did not appear to be affected by either leukoreduction or cold storage.

Platelets were routinely stored at 4°C until the 1980s, and appeared to be safe during this time. These storage conditions were phased out because of the decreased circulation time of cold-stored platelets compared to platelets stored at room temperature, in order to best serve patients requiring prophylactic transfusions.²¹ It was assumed, but not proven, that these would be as effective as cold-stored platelets for actively hemorrhaging patients. Taken together, the above evidence indicates that in actively bleeding patients, cold-stored platelets are likely to achieve faster hemostasis than room temperature-stored platelets, and are more likely to prevent re-bleeding in patients requiring high mean arterial pressure, such as spinal cord injury patients.

1.2 Overview of Clinical Studies

The change in standard practice from whole blood transfusion, to fractionation and component transfusion, occurred after the 1970s because of concerns over resource utilization and safety. However, there was no evidence documenting equivalence between whole blood and components for trauma patients, and new data is now suggesting that whole blood may be superior for obtaining hemostasis and oxygen delivery for the acutely bleeding trauma patient.²²

The first evidence that whole blood may be superior to component therapy for trauma patients comes from military studies in Iraq and Afghanistan using fresh whole blood (FWB). FWB was initially used as a source of platelets, in addition to PRBCs and

plasma, when platelets were not available in far-forward military settings.²³ A retrospective analysis of prospectively collected data from all transfused patients at 6 forward surgical teams comparing standard component therapy to component therapy with whole blood substituted for platelets found that when adjusted for confounding variables, patients who received FWB had a significant survival advantage.²³ Of note, a subgroup analysis of patients who received “universal-donor” group O FWB (49%) versus type-specific product found there was no difference in mortality between these groups, and that there were no transfusion reactions.

Similarly, a retrospective analysis of 354 combat casualties transfused at least one unit of PRBCs compared standard component therapy with PRBCs, plasma, and warm FWB.²⁴ Patients who received whole blood had significantly lower transfusion volume requirements, and received significantly less preservative and anticoagulant additive volume, compared to patients receiving standard component therapy. 24 hour and 30 day survival was significantly higher in the whole blood group.

On the civilian side, a recent randomized controlled pilot trial compared whole blood leukoreduced with a non-platelet-sparing filter and stored for up to 5 days at 1-6°C, supplemented with warm stored platelets, to regular component therapy in severely injured patients predicted to require large volume transfusion.¹ There was a trend towards decreased plasma and platelet requirements in the whole blood group in the on-protocol analysis. In post hoc analysis use of whole blood was associated with a reduction in the amount of transfusion when traumatic brain injury was excluded.

Current FDA regulations stipulate that whole blood must be type-specific. However, as reviewed by Spinella et al (7) and Berseus et al²⁵, there is convincing evidence that the risk of a hemolytic transfusion reaction from transfusion of low titer group O WB is minimal. As these authors point out, the US Army used low titer group O WB as a universal donor blood in the Vietnam conflict. Per their report, there was only one reported hemolytic transfusion reaction from transfusion of group O WB where a group A patient incorrectly received a unit that was labeled high titer. There were no reported hemolytic transfusion reactions following transfusion of low titer group O WB to non-group O patients. Berseus et al have reviewed the known literature on hemolytic transfusion reactions after transfusion of group O products to non-group O recipients and found that virtually no such reactions occur in association with low titer O products.²⁵ The authors concluded that “there is an overwhelming experience, particularly from the transfusion of low titer universal group O whole blood in the military service, showing that the frequency of severe hemolytic transfusion reactions is nearly negligible”.²⁵ Finally, Yazer et al have shown that it is safe to initiate resuscitation from hemorrhagic shock in male patients with low titer group O+ WB in a civilian trauma center. In this study, patients were transfused up to 2 units uncrossmatched group O positive WB

PI: [name]

leukoreduced using a platelet-sparing filter and stored at 1-6°C for up to 10 days for male trauma patients with hypotension due to hemorrhage. Outcomes were compared to historical controls. No adverse reactions and no laboratory evidence of increased hemolysis in the whole blood group was found.²⁶ That institution has now increased their initial transfusion of low titer group O+ WB to 4 units with similar results (personal communication). Our study seeks to build on this work by establishing efficacy of cold stored whole blood leukoreduced with a platelet sparing filter. Only low anti-A, anti-B group O-positive whole blood will be used as a universal donor in the proposed study. Platelets, which are not typically crossmatched, have occasionally resulted in hemolytic reactions after transfusion. In the 25 publications reviewed, all but one reaction resulted from a unit with a titer of >1:100 (saline) or >1:400 (antiglobulin); often, titers were >1:1000. Our study proposes to use a cutoff of <1:100.

There have been reports of hemolytic reactions when a patient initially transfused with unmatched group O whole blood later received type-specific transfusion. A similar situation is encountered in current massive transfusion protocols and hemolytic reactions are prevented using the following precautions. Currently when the patient's blood type is unknown during a massive transfusion activation at UCLA, sets of 6 group O PRBC units, 6 pre-thawed group A plasma units and 1 apheresis platelet unit are provided. Once the blood type of the patient is determined, the blood bank switches to providing type-specific products unless the patient's blood type is group B or AB (i.e. incompatible with the group A plasma); under this circumstance, the blood bank provides another set of 6 group O PRBC units and compatible plasma before switching to type specific PRBCs. We have not identified any hemolytic transfusion reactions using this approach. We intend to follow this same practice with the transfusion of low titer group O+ WB. If after receiving low titer group O+ WB the patient's blood type is found to be a type other than group O, the blood bank will provide a set of group O PRBC units and compatible plasma units, before switching to type specific PRBC units.

Providing further evidence of the safety of this approach, our institution participated in a multi-center study evaluating the safety of the use of thawed group A plasma in trauma patients.²⁷ This study evaluated trauma patients that received group A plasma as part of the initial resuscitation (354 B and AB patients and 809 A patients). The two study groups were comparable in terms of age, gender, TRISS probability of survival, and total number of blood products transfused. The study found that the use of group A thawed plasma during the initial resuscitation of injured patients of unknown ABO group was not associated with increased in-hospital mortality, early mortality or hospital length of stay for group B and AB patients compared to group A patients. Additionally, of the 17 participating centers, only 4 (24%) provide low-titer group A plasma; the other 13 centers do not perform titers of the plasma components. This

PI: [name]

experience indicates that transfusion of group A thawed plasma, regardless of anti-B titer, is safe. A manuscript reporting these findings was recently accepted by *Transfusion* (accepted March 15, 2017).

2 STUDY RATIONALE

The evidence described above indicates that low titer group O cold-stored whole blood stored for up to 10 days may be a superior product for obtaining hemostasis and maintaining oxygen delivery in hemorrhaging trauma patients in the emergent setting, compared with component therapy. A prior study has demonstrated the safety of this universal donor product in adult male civilian trauma patients²⁸; however, efficacy must be determined in a prospective civilian context.

The advantage of cold-stored whole blood may be due to several factors, or a combination of factors, including superior platelet function, lack of storage lesion, and decreased volume of preservative and anticoagulant additives. These factors will be evaluated in our study.

2.1 Risk / Benefit Assessment

As described above (See sections 1.1 and 1.2, Overview of Non-Clinical and Clinical Studies), low titer group O cold-stored whole blood stored for up to 10 days has been shown to be safe as a universal donor product. There is substantial evidence from literature spanning over 40 years, described above, that low-titer group O whole blood can safely be used as a universal donor product and retains hemostatic capacity. The risk of hemolytic reaction when a patient initially transfused with unmatched group O whole blood later receives type-specific transfusion is mitigated by using low titer whole blood and by requiring that patients who have received uncrossmatched group O whole blood must receive a further 6 units of type-specific plasma transfused prior to receipt of type-specific PRBCs to prevent a reaction. In the interim the patient will receive group O PRBCs. There is also evidence that whole blood may be a superior hemostatic product compared to component therapy, and that it may reduce transfusion requirements, development of coagulopathy, and ultimately mortality. The risk-benefit profile of whole blood transfusion is therefore quite favorable. The evidence for this analysis is described extensively in sections 1.1 and 1.2, Overview of Non-Clinical and Clinical Studies.

PI: [name]

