15.3 Analysis of Primary Endpoint

Primary analysis compares volume of blood products transfused in the first 24 hours of admission in patients without severe TBI (severe TBI is defined as GCS \leq 8 and evidence of brain injury on imaging) receiving whole blood versus component therapy during initial resuscitation.

For continuous variables including the primary endpoint, the statistical method will depend on the distribution of the data. If the data appears to follow a normal distribution, a t-test will be used, otherwise, a nonparametric Wilcoxon rank sum test will be used.

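### Sections 1.2 and 2.1 of the protocol state the plasma precaution after whole blood in two incompatible ways, and the treatment section does not settle which applies

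*Protocol*

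**What the plan says.** Section 1.2 first describes current practice under component therapy when the patient's group is unknown: "sets of 6 group O PRBC units, 6 pre-thawed group A plasma units and 1 apheresis platelet unit are provided". Once the group is known, the blood bank moves to type-specific products, except that group B and AB patients first get a further set of group O red cells with compatible plasma. For whole blood the section adds "We intend to follow this same practice with the transfusion of low titer group O+ WB". It then ties the precaution to the recipient's group, with the trigger worded as "the patient's blood type is found to be a type other than group O". The action that follows in that case reads "the blood bank will provide a set of group O PRBC units and compatible plasma units, before switching to type specific PRBC units".

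Section 2.1 presents the precaution as something already fixed. One mitigation of hemolytic risk is the low titer. The other is a requirement whose population is worded as "requiring that patients who have received uncrossmatched group O whole blood", with no limit by the recipient's own group. What it demands of those patients is that they "must receive a further 6 units of type-specific plasma transfused prior to receipt of type-specific PRBCs". It continues: "In the interim the patient will receive group O PRBCs".

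Section 8 (Study Treatments) covers product formulation, supply, the whole blood cap, dispensing and administration. It does not mention the precaution. The synopsis says only that transfusion after whole blood continues as component therapy at 1:1:1.

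On the endpoint, Section 15.3 states: "Primary analysis compares volume of blood products transfused in the first 24 hours of admission". It does not separate plasma given under the switching precaution from any other plasma.

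**The concern.** Section 2.1 uses the precaution to support its favorable risk-benefit conclusion, and Section 12.5 makes a hemolytic reaction after whole blood a reason to suspend the study and, if confirmed, to stop it. A safeguard with that role should be stated once, where staff look for treatment instructions. Here it appears only in background and rationale, in two versions. A blood bank working from Section 1.2 could act correctly by that text and still breach Section 2.1.

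There is also a smaller statistical consequence. The primary endpoint is total blood-product volume over 24 hours, and the sample size rests on an expected reduction in red cells and plasma. If the precaution reaches one arm more often than the other, part of the difference in volume may reflect the switching procedure and not the patient's bleeding.

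**Working it through.** **Step 1. The two statements side by side.**

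| Element | Section 1.2 | Section 2.1 |
|---|---|---|
| Who is covered | Whole blood recipients found not to be group O | All recipients of uncrossmatched group O whole blood |
| Which plasma | Compatible | Type-specific |
| How much | A set; 6 plasma units only by inference from current set size | 6 units, explicit |
| Obligation | Blood bank supplies it | Must be transfused |
| What it precedes | Switch to type-specific red cells | Receipt of type-specific red cells |
| Red cells meanwhile | Group O, as part of the set | Group O |

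The last two rows agree. The number can be made to agree by inference. The other three rows do not agree.

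**Step 2. Which patients each text reaches.** This assumes that the current practice in Section 1.2 continues to govern the component arm.

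| Recipient's group | Whole blood, 1.2 | Whole blood, 2.1 | Component therapy, 1.2 |
|---|---|---|---|
| O | Not triggered | Covered by the wording | Direct switch |
| A | Set before switch | 6 plasma units before switch | Direct switch |
| B or AB | Set before switch | 6 plasma units before switch | Set before switch |

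Group A patients are treated differently by arm under either version. Section 2.1 read literally adds group O whole blood recipients. Group B and AB patients meet a precaution in both arms. The arms therefore differ in degree.

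**Step 3. What this could do to the endpoint.** Let g be the share of whole blood patients who go on to type-specific red cells, and q the share who are not group O. Taking a set as 6 plasma units, the average number of units falling under the precaution per whole blood patient is:

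- Section 2.1: 6 × g
- Section 1.2: 6 × g × q

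Neither g nor q is in the documents. With g = 0.5 and q = 0.4 to 0.6, both assumed, the results are 6 × 0.5 = 3.0 units against 6 × 0.5 × 0.4 = 1.2 to 6 × 0.5 × 0.6 = 1.8 units. So the choice of text matters to how much plasma is governed by the precaution.

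These are units covered, not extra units. Let f be the share of whole blood patients for whom the 6 units are truly additional and fall within 24 hours. Mean volume in that arm then rises by 6 × f units: 0.6 at f = 0.1, 1.5 at f = 0.25, and nothing at f = 0. The documents give no value for f. They also do not say when the switch occurs relative to 24 hours.

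**Step 4. Whether it can be scaled to the planned effect.** The planned number reproduces as 49 − 18 = 31 per group. With 31 per group, 80% power and a two-sided t-test at 0.05, the implied detectable difference is 0.72 SD. The protocol gives neither the SD nor the effect in units or mL, so 6 × f cannot be set against it without assuming both.

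**The case against.** The strongest case on the other side is that this is loose wording and not a conflict. Section 2.1 is a summary that refers back to Section 1.2. A set contains 6 plasma units, so the number agrees. Type-specific plasma is one kind of compatible plasma. For a group O recipient the interim and the type-specific red cells are both group O, so the wider coverage in Section 2.1 has little practical content.

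Part of this stands. The number can be harmonized, and the difference over group O recipients may rarely matter at the bedside. The rest does not stand. Plasma can be compatible without being of the recipient's own group; such plasma satisfies Section 1.2 and fails Section 2.1. Supplying a set is also not the same as requiring that its plasma be transfused before the switch. Staff should not have to infer which reading governs.

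A reader might go further and infer that Section 2.1 mandates extra volume in the whole blood arm only, inside the primary endpoint. The documents do not support this, for three reasons:

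- Section 2.1 sets a condition for receiving type-specific red cells. A patient who needs no more red cells, or stays on group O cells, need not receive the 6 units.
- Section 1.2 gives an analogous set to group B and AB patients on component therapy.
- Transfusion after whole blood is at 1:1:1, so the patient may receive this plasma in any case.

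A reader might also set 6 units at an assumed 200 to 250 mL (1.2 to 1.5 L) over an assumed SD of 2.5 to 4 L, obtain 0.30 to 0.60 SD, and compare that with 0.72 SD. The first figure is a shift within an affected patient, on assumed inputs. The second is a difference between arm means. The two are not comparable until the first is multiplied by the affected share, which is unknown and may be zero.

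**Conclusion.** The contradiction between Sections 1.2 and 2.1 is established from the text alone. They disagree on who is covered, which plasma is meant, and whether it is supplied or must be transfused; the number is explicit in only one of them. Because this is a stated safeguard against an event that can stop the study, and Section 8 is silent on it, the two sections must be reconciled.

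The effect on the primary endpoint is a secondary note. On the assumption that current practice continues in the component arm, the precaution reaches more whole blood than component recipients under either wording, group A patients being the clear example. Any truly additional plasma within 24 hours would raise whole blood volume and so work against showing a reduction. Its size cannot be computed, because the SD, the planned effect in units, the plasma unit volume, the blood-group mix, the share who switch and the timing of the switch are all absent. It may be zero.

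**What to change.** Replace the two versions with one statement in Section 8, and have Sections 1.2 and 2.1 refer to it. The statement should settle who is covered, which plasma is meant, how many units, whether they are to be supplied or transfused, and how this relates to the red cell switch. It should also say what applies to component therapy patients. The content is for the sponsor and the transfusion committee to decide; none is proposed here.

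A sensitivity analysis that removes units given under the precaution is not requested. Plasma that the whole blood strategy requires is arguably part of that strategy's product use, so excluding it would answer a different question. In a patient on 1:1:1 therapy it would also be hard to say which units were given for which reason. It is enough for the interpretation of the primary result to acknowledge that such plasma counts in the endpoint and in which direction it could act.

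The cost is a wording amendment with IRB approval under Section 17.1. Sample size, data collection and the primary analysis are unchanged.
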